An *a priori* computer-generated stratified block randomization list will be used to assign patients to each of the 4 parallel fixed dosing schedules (allocation ratio 1:1:1:1, total subjects = 120). To ensure randomization of equal number of subjects to both nebulizers, block size of 8 will be used. To ensure equitable representation of gestational ages, GA stratum-specific randomization lists will be generated. Stratified block randomization will ensure balanced and independent distribution of participants within each dose group, avoid systematic differences between dose groups with respect to known or unknown confounding baseline variables, remove selection bias and control temporal trends^{2,62-66}. The balance resulting from blocked stratification can improve the power of trials by reducing unwanted variation, reduce Type I and II error rates, increase efficiency, and improve subgroup analyses.

The structure of Table 10 shows breakdown of the sample by confounding variables in rows (GA [stratifying factor] & nebulizer type [blocking factor]) with columns representing treatment groups. Therneau showed that balance in covariates begins to fail when the number of blocks approaches half the sample size (n/2)^{64,67}. Therefore studies using stratified assignment should not attempt to balance on

Table 10: Stratified Block Randomization of Sample

GA Group (Strata)	Nebulizer Device (Blocks)	Dosing Schedule			
		I	II	III	IV
24 0/7 – 28 6/7 (Extremely PT) ⁶¹	MiniHeart	5	5	5	5
	AeroNeb	5	5	5	5
29 0/7 – 32 6/7 (Very PT)	MiniHeart	5	5	5	5
	AeroNeb	5	5	5	5
33 0/7 – 36 6/7 (Moderately PT)	MiniHeart	5	5	5	5
	AeroNeb	5	5	5	5
Total		30	30	30	30

more than 2 to 3 important factors. In this study we have balanced 2 important factors (GA, nebulizer type); the resulting number of blocks (3 GA strata x 2 nebulizers x 4 dosing schedule groups=24) is <n/2 (120/2=60).

Multiple births, common in this premature population, will be randomized independently and not as a unit as the latter can lead to bias in the randomization process.

1.1.4.7. Allocation Concealment:

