In our unit, infants ≤ 32 weeks GA with RDS being treated with NIV receive *caffeine* shortly after starting NIV as recommended/reported in the literature^{7,74}. Enrolled infants will receive the 1st dose of caffeine prior to study intervention as standard clinical care in this study. This will prevent confounding of assessment of efficacy of study intervention both within and between subjects by caffeine effect. Caffeine therapy will consist of an intravenous loading dose of 20 mg/kg caffeine citrate/kg body weight followed by a daily maintenance dose of 5 mg/kg; duration of treatment will be determined by the clinical team.

Recommended criteria for intubation will be same as defined under Exit criteria (Section 3.6.5). If in an enrolled infant respiratory distress progresses and criteria for intubation are met prior to the institution of nebulized surfactant, the infant will exit the study and rescue therapy will be instituted immediately. *Recommended criteria for adjustments to ventilator settings* on conventional and high frequency ventilation include maintaining PaO₂ 50 to 70 mmHg, or oxygen saturation 90% - 95%, and PaCO₂ <65 mmHg.

Infants who are enrolled in the study and subsequently require intubation may receive *intratracheally instilled surfactant* at the discretion of the clinical team. It is not necessary to wait 6 hours from last dose of AS to administer the first dose of intratracheal surfactant if other clinical criteria are met⁷⁵. *Criteria for subsequent clinical intratracheal surfactant doses* (drawn from a clinical stock of Survanta) will include need for MV with FiO₂ >0.30 and mean airway pressure >7 cm H₂O for ≥ 20 min at ≥ 6 hours from last dose^{69,76}.

It will be recommended that extubation be attempted within 24 hours after the infant meets all of the following criteria: PaCO₂ <65 mm Hg, pH >7.20, SpO₂ 90-95% with an FiO₂ < 0.50, mean airway pressure <10 cm of water, ventilator rate < 20 breaths per minute, an amplitude of less than twice the mean airway pressure if high-frequency ventilation is being used, and hemodynamic stability⁷⁵.

All PT neonates with respiratory distress requiring NIV receive a *chest radiograph* (CXR) as standard clinical care; a CXR is not mandatory prior to enrollment for this study. *Echocardiography* and *cranial sonography*, will be performed at the discretion of the clinical team based on infants GA and clinical status.

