The Phase I/II Clinical Trial under this protocol does not have a placebo group; all randomized subjects receive active treatment. Preterm infants 24 0/7 - 36 6/7 weeks gestation that were admitted to the Hutzel Women's hospital NICU during the enrollment period (Dec 10, 2014 to Aug 31, 2017) will serve as historical controls to be able to compare intubation rates in infants enrolled and those not enrolled in the study. This will also allow comparison of other in-hospital outcomes, give an idea of numbers of infants available for the future Phase III clinical trial and the optimal time for administering study intervention.

1.1.6. Exit Criteria/Treatment Failure Criteria:

It will be suggested that infants be intubated and receive MV if they met 2 or more of 5 failure criteria:

- i). worsening clinical signs of respiratory distress (increasing tachypnea; expiratory grunting; intercostal, subcostal, and/or sternal recession);
- ii). apnea treated with positive pressure ventilation (PPV) by mask on 2 or more occasions in 1 hour;
- iii). FIO₂ >0.5 to maintain pulse oxygen saturations 90%-95% for >30 minutes;
- iv). pH <7.2 on 2 arterial or capillary blood gases taken >30 minutes apart; and
- v). partial pressure of CO₂ (PCO₂) of >65 mm Hg on 2 CBG/ABGs taken 30 minutes apart.

1.1.7. Primary outcome:

1.1.7.1. Safety:

Safety will be assessed by monitoring for oxygen desaturations, apnea, bradycardia/tachycardia, hypotension, air leaks, need for resuscitation, nasal trauma score, agitation, blockage of nasal prongs or NIV circuit, and cerebral oxygen saturation prior to, during and after study drug administration (Adverse Event [AE] Monitoring Form, Appendix VII [Table A8, A9]). Other safety measures that will be monitored include increased secretions requiring suctioning, coughing/gagging, surfactant reflux from nose/mouth, rainout in ventilator tubing, dislodged nasal prongs, abdominal distension, and nebulizer malfunction. It is expected that need for intubation is likely to be higher in the lower GA group strata.

1.1.7.2. Feasibility:

We define feasibility for this pilot RCT as the ability to:

- i). Safely deliver AS to PT infants with RDS without interrupting clinical care because of clogged nasal prongs or ventilator alarms related to inline nebulization. At the end of AS a Feasibility Questionnaire will be administered to bedside nurses & respiratory therapists to evaluate this (Appendix VIII).

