In this safety, feasibility and dose finding Phase II trial, 30 infants will be assigned to each of the 4 dose schedules^{4,88}. The aim of phase II trials is to explore different doses, evaluate safety & tolerability, and obtain early indication of efficacy⁸⁸. The dose-safety relationship is more important than the dose-efficacy one as efficacy is irrelevant if the dose is unsafe⁸⁹. Phase II trials are generally inadequate with respect to size, outcome, precision, and control of bias to provide formal proof of efficacy^{3,90}. Rather these trials provide baseline data, potential primary outcome and effect size justifying the larger, longer, and more expensive Phase III trial. *Recognizing that our Phase II trial is not powered for efficacy, sample size calculations based on precision of the estimate of the primary outcome & the null hypothesis and error rate are presented below.*

Sample Size Based on Precision for the Primary Efficacy Outcome:

The efficacy goal of Phase II studies is typically to estimate a clinical endpoint with a specified precision. The primary efficacy outcome in this study is the need for intubation & MV within 72 hours of AS. Using the normal approximation to the binomial as described by Piantadosi⁸⁸ ($w = Z_{\alpha} \times \sqrt{p(1 - p)/n}$; or more simply $n=1/w^2$ for estimated proportions (p) ranging from 0.2 to 0.8, where Z_{α} is the quantile from the normal distribution corresponding to the two-sided probability, n =sample size, w =width of the 95% confidence interval [CI] or precision), a sample size of 30 per dosing schedule group will allow evaluation of a failure rate of 0.25 - 0.4 with 95% CI of ± 0.15 to ± 0.17 (15 to 17% precision) (Table 12). The precision of this estimate is increased if we collapse the dilution groups corresponding to dose of 100 mg/kg & 200 mg/kg (<12%) or consider our entire sample of 120 subjects all of whom receive the study intervention (<9%).

Table 12: Sample Size & Precision for various proportions of primary efficacy outcome:

Sample Size	Rate	Precision for Estimating Outcome		
		95% CI		Precision
		Lower	Upper	
30 (for each dosing Schedule i.e. I, II, III, IV)	0.25	0.13	0.43	$\pm 15\%$
	0.3	0.17	0.48	$\pm 15\%$
	0.35	0.21	0.53	$\pm 16\%$
	0.40	0.25	0.58	$\pm 17\%$
60 (for each dose group 100/kg vs. 200 /kg)	0.25	0.16	0.37	$\pm 11\%$
	0.3	0.2	0.45	$\pm 12\%$
	0.35	0.24	0.48	$\pm 12\%$
	0.40	0.29	0.53	$\pm 12\%$
120 (for the whole group)	0.25	0.18	0.33	$\pm 8\%$
	0.3	0.23	0.39	$\pm 8\%$

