Data will be analyzed according to the intention-to-treat principle using SAS and PASW (IBM Inc.). We will report descriptive statistics for demographic, clinical and respiratory support data at baseline and over time for the entire sample and for the 4 dosing schedule groups (Appendix IX [Table M1, M2]). In addition, three subgroup analyses are planned – according to dose regardless of dilution (100 vs. 200 mg/kg), GA strata, nebulizer device using logistic regression incorporating an additional treatment-by-subgroup interaction term.

Analysis plan to address Aim #1 – Safety and Feasibility Assessment: Safety will be assessed by quantifying and comparing the AEs and their severity for the total sample and across the dosage/dilution groups and two types of nebulizers. Indicators include cardiorespiratory responses, blockage of NIV circuit and cerebral oxygen saturation (Appendix IX [Table M5]). Descriptive statistics (mean, standard deviation, proportion, inter-quarter range [IQR]) will be used to quantify these indicators; *confidence intervals will be preferred to hypothesis testing* as considerable imprecision is expected arising from low frequencies of these AEs³. ANOVA or *t*-test (continuous measures) and χ^2 test (categorical variables) will be used for comparative analyses though we may not find statistically significant differences. Paired *t*-test will be used to compare heart rate, respiratory rate, blood pressure, SpO₂, PCO₂, cerebral oxygenation (RCO₂, cFTOE), ACoRN score and nasal exam score before and after AS. These parameters will also be compared between infants who get intubated within 72 hours of study intervention and those who do not; and before and after intubation within subjects that get intubated. Feasibility will be assessed by quantifying and comparing the percentage of infants who tolerate the treatment procedure and responses of the clinical nurses and respiratory therapists on the feasibility questionnaire (Appendix IX [Table M6]). Because of the high inherent variability of these factors and small effect sizes, we do not expect to show significant differences between groups given our sample size. However this information will be useful in making the final decision to proceed with a Phase III RCT.

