A number of secondary outcomes will be assessed using the same methodology. Vital signs, SpO₂, FiO₂, NIV parameters (pressure, rate, flow) and ABG/CBG components (pH, PO₂, PCO₂) will be evaluated before and after study intervention (paired *t*-test) and over time (Longitudinal data analysis). Other secondary outcomes include change in surfactant activity in gastric aspirates, changes in cerebral oxygenation, diagnosis of PDA, need for blood transfusions, postnatal growth, duration of respiratory support, length of hospital stay, and incidence of complications of prematurity including IVH, sepsis, NEC, BPD, pneumonia, ROP, and death. We will describe and compare primary and secondary outcome data overall and by dosing schedule, and in three pre-planned subgroup analyses – by dose regardless of dilution (100 mg/kg vs 200 mg/kg), GA group stratum and nebulizer type, recognizing that we may observe trends of differences between groups without having power to determine statistical significance. We will report dichotomous secondary outcome data as proportions and compare the groups using χ^2 and nonparametric tests. We will report secondary continuous outcome data as mean (SD) for normally distributed data and median (interquartile range [IQR]) for skewed data, and will compare the groups by using parametric (*t*-test, ANOVA) and nonparametric tests (Mann-Whitney U test, Wilcoxon's test) as appropriate. Pairwise group comparisons of the four dosing schedule groups will also be performed, although we may lack power to detect significant differences. In a final posthoc analysis, we will compare infants who received intubation within 72 hours to those who did not to understand risk factors for intubation and their modification by study intervention. This analysis will be presented for the entire group and by dosing schedule group. In *adjusted analyses*, dosing schedule, GA group, nebulizer type, mode of NIV, antenatal steroids, and presence of PDA or IVH will be included as covariates recognizing that these analyses are exploratory and need to be interpreted cautiously. We will consider a p value of <0.05 for statistical significance. Mock tables for the planned analyses are presented in Appendix IX.

Recommendations for statistical analyses by the Data Monitoring Committee (DMC) during the conduct of the trial:

1. Additional factors associated with intubation in enrolled infants – clinical team, time of day/shift, clinical variables (e.g. sepsis, NEC)

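### Before-after paired t-tests have no untreated control, and the planned comparisons of randomized schedules omit the outcome's baseline value

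*Combined protocol and SAP*

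**What the plan says.** Section 1.1.12, under Aim #1, states that a paired t-test "will be used to compare heart rate, respiratory rate, blood pressure", SpO₂, PCO₂, RCO₂, cFTOE, "ACoRN score and nasal exam score before and after AS". The secondary-outcome text after Aim #3 lists vital signs, SpO₂, FiO₂, NIV settings and blood gas components, which "will be evaluated before and after study intervention", again by paired t-test, and adds a longitudinal analysis without specifying a model. The significance level is 0.05.

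Section 1.1.5 states: "The Phase I/II Clinical Trial under this protocol does not have a placebo group; all randomized subjects receive active treatment". Randomization is between four active schedules (Section 1.1.4.6: "allocation ratio 1:1:1:1, total subjects = 120"; Section 1.1.10: "30 infants will be assigned to each of the 4 dose schedules").

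For comparisons between groups, Aim #1 names ANOVA or t-test and χ², which "will be used for comparative analyses though we may not find statistically significant differences". The adjusted analyses list schedule, GA group, nebulizer, NIV mode, antenatal steroids, and PDA or IVH. The baseline value of the outcome is not on that list, although Table 9 and Section 1.1.4.10 show that baseline measurements are taken.

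On caffeine, Section 1.1.4.9 has the first dose given before AS and concludes: "This will prevent confounding of assessment of efficacy of study intervention both within and between subjects by caffeine effect".

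**The concern.** Infants enter on the first day of life with two or more signs of respiratory distress and recently started NIV (Section 1.1.2). Their physiology can move over the following hours for reasons unrelated to AS. A paired test asks only whether the mean changed. It cannot separate an AS effect from postnatal transition, NIV, caffeine or regression to the mean. For safety measures the risk runs the other way too, since natural improvement could mask a harmful effect. Section 1.1.12 says that the Aim #1 information will inform the decision to proceed to Phase III.

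The trial does have randomized groups, and for these the baseline value is a free source of precision. The plan concedes several times that between-group comparisons may lack power, yet it does not say that this covariate will be used.

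**Working it through.** The documents give no SD, pre-post correlation or expected change for these measures, so there is no stated figure to reproduce. The drift and correlation values below are assumptions, shown as ranges.

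**1. Paired test with no AS effect.** With natural drift d in SDs of the paired difference, the rejection rate is about Φ(d√n − 1.96). At n = 120 (Section 1.1.4.6), √120 = 10.95:
- d = 0.1: Φ(1.095 − 1.96) = Φ(−0.865) = 19%
- d = 0.2: Φ(2.191 − 1.96) = Φ(0.231) = 59%
- d = 0.3: Φ(3.286 − 1.96) = Φ(1.326) = 91%

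Within one schedule (n = 30), d = 0.3 gives Φ(1.643 − 1.96) = Φ(−0.317) = 38%. The rate rises with n, and Section 1.1.10 later raises the Phase II total to 220, including an allowance for screen failures.

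**2. Selection at entry alone.** The paired test was simulated at n = 120 with no AS effect and no drift. Baseline values were truncated to mimic entry on respiratory distress (1,500 repetitions per setting).

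| Assumed truncation | r = 0.5 | r = 0.7 | r = 0.9 |
|---|---|---|---|
| none | 6% | 6% | 5% |
| 1 SD below the mean | 37% | 23% | 12% |
| at the mean | 99.5% | 94% | 50% |

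In the same data a baseline-adjusted comparison of four schedules kept its type I error between 4.3% and 5.9%. That simulation used the same before-after interval in every schedule (see step 4).

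**3. Gain from the baseline covariate.** With equal variances before and after, relative variances of a between-schedule contrast are 1 for post-AS values alone, 2(1 − r) for change scores and 1 − r² for the adjusted model.
- Against post-AS values alone, the cut is r²: 9%, 25% or 49% at r = 0.3, 0.5 or 0.7.
- Against change scores, the ratio is (1 − r²)/[2(1 − r)] = (1 + r)/2. At r = 0.7 this is 0.85, a 15% cut.

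The detectable difference at 80% power, two-sided 0.05, with 30 per schedule is (1.96 + 0.84)·√(2/30) = 0.72 SD for post-AS values alone. Multiplying by √(1 − r²) gives 0.63 SD at r = 0.5 and 0.52 SD at r = 0.7. With 60 per dose it is 0.51 SD, against 0.44 and 0.37 SD.

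**4. When is 'after'?** The post-AS blood gas is timed from the end of nebulization (Section 1.1.4.10). Section 1.1.4.3 gives total volumes of 4 + 4 = 8 ml/kg for Schedule I and 8 + 16 = 24 ml/kg for Schedule IV. The jet nebulizer delivers 8 ml/hr (Section 1.1.4.4), so nebulization takes 8/8 = 1 h/kg and 24/8 = 3 h/kg. If values drift naturally, end-of-AS values differ between schedules through elapsed time alone, even after baseline adjustment.

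**5. Caffeine.** Section 1.1.4.9 puts caffeine before AS. Section 1.1.4.10 records the blood gas and vital signs before or at enrollment. Nothing fixes whether these come before or after caffeine. If they come before, the caffeine effect lies inside the before-after interval.

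**6. Ordinal scores.** With no true change, the paired t-test on assumed 4-level (mostly zero) and 8-level scores had type I error of 3.7% to 5.1% at n = 30 and 120.

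**The case against.** The paired tests are not the plan's sole or decisive analysis. Safety is also compared across schedules and nebulizers, with confidence intervals preferred to tests. Longitudinal and adjusted analyses are planned, and evidence of efficacy is defined by the intubation rate against 0.5. Nowhere is a significant paired test said to prove an AS effect. Clinicians are asked to hold respiratory support constant until the post-AS gas, and the DMC asked for control of baseline ventilation mode and for detailed caffeine data. Some outcomes are defined as changes, which already use the baseline. All of this stands and confines the point to labelling and model specification. It does not remove it: a confidence interval around an uncontrolled change carries the same bias, and holding support constant does not stop natural course or regression to the mean.

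A reader might infer more than the documents support:
- **That the paired test would be significant even if AS did nothing.** This depends on the drift assumed; at 0.1 SD the rate is about 19%.
- **That randomized comparisons can replace the before-after estimate.** Every arm receives AS, so they answer a different question.
- **That caffeine certainly falls inside the interval.** The order of measurement and dose is not fixed.
- **That t-tests on the two scores are invalid.** Their scales are in an appendix that is not part of the available text, and step 6 shows little harm.

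**Conclusion.** The point holds in limited form. The before-after tests are uncontrolled, and significance at 0.05 cannot be attributed to AS. Under no AS effect the rejection rate at n = 120 is about 19% to 91% for an assumed drift of 0.1 to 0.3 SD of the paired difference. The between-schedule and adjusted analyses do not name the outcome's baseline value. Naming it would cut variance by 9% to 49% against post-AS values alone (r = 0.3 to 0.7), and by less against change scores (15% at r = 0.7). The documents do not say which of the two would be analyzed. The claim that prior caffeine prevents within-subject confounding is not secured by the procedures described.

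The effect is on exploratory physiological and safety measures. The adjusted contrasts inform the choice of dose and dilution and say nothing about AS against no AS. The primary outcome, intubation within 72 hours, does not use these tests.

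**What to change.** 1. In Section 1.1.12, under Aim #1 and in the secondary-outcome text, report before-after changes as descriptive, with confidence intervals and no attribution to AS.
2. For continuous physiological measures, compare the randomized schedules with a linear model containing the baseline value, dose, dilution, GA stratum and nebulizer. Use measurements at a stated common time from the start of AS, late enough for the longest nebulization to be over, or specify the planned longitudinal analysis with time counted from that start. The longitudinal form suits blood gases better, because their scheduled post-AS sample follows the end of nebulization. State how values after intubation are handled.
3. Limit the caffeine statement in Section 1.1.4.9 to between-subject comparisons, and report the time of the first dose relative to the baseline measurement. The DMC's request for caffeine data already points this way.
4. Optionally, name a rank-based test for the ACoRN and nasal scores.

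The cost is SAP wording and some programming. Baseline values are already collected, and vital signs are recorded every 15 minutes during aerosol. No additional infants are needed.

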The DMC met on 02-22-2017 and recommended continuing subject accrual in the lowest GA Stratum (I) till Dec 2017. In addition, the DMC recommended continuing subject accrual in the two higher GA Strata subject to availability of resources; enrollment in excess will increase power and confidence in the results.

We proposed increasing the sample size by 40 to account for additional infants to be enrolled in the two higher GA strata till Dec 2017 or when 40 subjects have been accrued in Stratum I, whichever comes earlier. In addition we requested that the sample size for the study be increased by 20 to accommodate for current and future screen failures (estimating a maximum of 10 screen failures in the future). These two changes will increase the total sample size of the Phase II portion of the study to 220 subjects, and overall sample size of the study including the 17 subjects enrolled in the Phase I portion of the study will be 237.

1.1.11. Patient Population Available for the Single Center Phase II study:

This study will be performed primarily at HWH, a level III neonatal intensive care unit (NICU) and high risk maternal referral center. Numbers of infants 24^{0/7} – 36^{6/7} weeks GA treated for RDS are estimated from the data presented in Section 3.3.3. The goal is to enroll 120 subjects over 3 years. Given the statistics for the past 2 years an adequate population of infants is available even after considering a continued trend for declining birth rate, 10% need for intubation in delivery room and a conservative estimate of consent rate of 50%.

Table 14: Patient Population Available for Study:

GA	Admissions at HWH			Estimates of infants requiring treatment for RDS (%)*		Estimates of Projected # of infants requiring treatment for RDS at HWH (n)			
						Over 2 years		Over 3 Years	
	2011	2012	Total	Lower	Higher	Lower	Higher	Lower	Higher
24-28	76	76	152	0.38	1.00	58	152	87	228
29-32	120	103	223	0.27	0.62	60	138	90	207
33-36	462	462	924	0.10	0.18	88	166	132	249
Total	658	641	1299			206	457	309	685

* based on Table 2; shaded rows represent population of interest for this study

1.1.12. Statistical Analyses:

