Analysis plan to address Aim #2: - Determination of Optimal Dilution and Dosage of AS: The optimum dose is one that produces low toxicity while nearly maximizing the biological response⁸⁹. The optimal dosage will be determined by comparing levels of adverse responses, feasibility items and primary and secondary efficacy treatment outcomes (rates of intubation, diagnosis of PDA, need for blood transfusions, postnatal growth, duration of respiratory support, length of hospital stay, and incidence of complications of prematurity including IVH, sepsis, pneumonia, BPD, NEC, ROP, and death) across the four dosing schedules (Appendix IX, Mock Tables). The optimal dosage/dilution will be the one with the minimum level of adverse responses and highest clinical treatment outcomes.

Analysis plan to address Aim #3 - Short-term efficacy of AS: The primary outcome variable for short-term efficacy is the need for intubation & MV within 72 hours of AS. We will estimate the unconditional probability of benefit for the four dosing schedule groups (I, II, III, IV), the 2 dose groups (100 vs. 200 mg/kg) and the entire study cohort of 120 subjects. We will also compare with reported rates of intubation in historical controls (50%). A special χ^2 test to compare sample proportion with population proportion will be conducted to test the study hypothesis that AS is efficacious. In the comparison analysis, different dosages/dilutions will also be considered as weight using the “optimal” dosage/dilution obtained from Aim #2 as reference. A significantly lower rate of intubation in infants treated with AS in this study as compared to the reported rate of ~0.5 at $p < 0.05$ level (two-sided) will be used as evidence supporting the efficacy of AS. However, it is likely we may not

have power to achieve statistically significant results. Nevertheless these preliminary efficacy data will be crucial in determining outcome measures and effect size for the definitive placebo-controlled Phase III trial.

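### The 'optimal' schedule is chosen partly on intubation and then serves as reference for intubation in the same infants, so its benefit is expected to be overstated by about 2 to 9 points

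*Combined protocol and SAP*

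**What the plan says.** All of this is in the combined protocol and SAP.

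- **Selection (Section 1.1.12, Aim #2).** The schedules are compared on adverse responses, feasibility items and "primary and secondary efficacy treatment outcomes (rates of intubation, diagnosis of PDA" and others. The decision rule is: "The optimal dosage/dilution will be the one with the minimum level of adverse responses and highest clinical treatment outcomes". No weights or tie-break are given.
- **Reuse (Section 1.1.12, Aim #3).** "The primary outcome variable for short-term efficacy is the need for intubation & MV within 72 hours of AS". In the comparison analysis, dosages and dilutions also enter as a weight, with the optimal "dosage/dilution obtained from Aim #2 as reference". No model or test is named for this step.
- **Onward use.** Section 1.1.7.3 says the data will help select the schedule for Phase III. Aim #3 adds that "these preliminary efficacy data will be crucial in determining outcome measures and effect size for the definitive placebo-controlled Phase III trial".
- **Sizes.** Section 1.1.4.6 gives "allocation ratio 1:1:1:1, total subjects = 120", and Section 1.1.10 says "30 infants will be assigned to each of the 4 dose schedules". The later amendment in Section 1.1.10 raises the "total sample size of the Phase II portion of the study to 220 subjects".

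Section 1.1.12 contains no shrinkage, split sample, bias-adjusted estimate or multiplicity control.

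**The concern.** When a schedule wins partly because its observed intubation rate is low, some of that low rate is chance. The same chance is counted again when the schedule becomes the yardstick for intubation in the same infants. Three results are exposed: contrasts between the other schedules and the chosen one, the chosen schedule's own rate, and that rate's comparison with the historical 0.5. The chosen schedule is the candidate for Phase III, so its own rate is a natural number to reach for when planning that trial. An optimistic rate gives too small a trial.

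**Working it through.** **1. The plan's own figure.** Table 13 gives 81.8% power for 0.25 against 0.50 at n=30. The arcsine formula is Φ(2√n·|arcsin√0.50 − arcsin√0.25| − 1.960). With 2 × √30 × (0.7854 − 0.5236) = 2.868, this is Φ(0.908) = 81.8%. The figure reproduces, but it applies to one schedule named in advance, not to the best of four.

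**2. Inputs.** Four schedules; n=30 each (Section 1.1.10); failure rates 0.25 to 0.40 (Table 12); historical rate 0.5. For the amended size, (220 − 20 screen failures)/4 = 50 per schedule. Assumptions not in the plan: independent schedules, equal true rates unless stated, the weight w given to intubation, and a Phase III control rate of 0.50.

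**3. Upper case: selection on intubation alone.** For X ~ Bin(n, p), the expected lowest of four observed rates is (1/n) Σ P(X > x)⁴, summed over x = 0 to n.

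| True rate | n=30: expected lowest (bias) | n=50: bias |
|---|---|---|
| 0.25 | 0.171 (−7.9 points) | −6.2 |
| 0.30 | 0.216 (−8.4) | −6.6 |
| 0.35 | 0.262 (−8.8) | −6.9 |
| 0.40 | 0.309 (−9.1) | −7.1 |

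**4. Intubation as one element of a composite.** Selection score: w × standardised intubation rate + √(1 − w²) × independent noise, lowest score wins (simulation). At true rate 0.35:

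| w | Bias, n=30 | Bias, n=50 |
|---|---|---|
| 0 | 0 | 0 |
| 0.25 | −2.2 | −1.7 |
| 0.5 | −4.4 | −3.4 |
| 0.75 | −6.6 | −5.1 |
| 1 | −8.8 | −6.9 |

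**5. Unequal true rates.** With 0.40/0.35/0.30/0.25, n=30 and w=1, the bias is −6.5 points. With 0.45/0.40/0.35/0.25 it is −5.1 at n=30 and −2.8 at n=50.

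**6. Contrasts and tests (n=30, equal rates, w=1).** If the chosen schedule sits b below the truth, the other three average b/3 above it, so the apparent gap is 4b/3. At b = 8.8 that is about 11.7 points where none exists. At least one of the three unadjusted pairwise tests against the chosen reference is significant in 19–20% of runs, against about 12% when the reference is chosen independently of intubation. Against 0.5 with no effect, the exact test rejects in favour at 9 or fewer of 30. That has probability 2.1% for one named schedule and 1 − (1 − 0.0214)⁴ = 8.3% for the best of four.

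**7. Phase III, if sized on the selected raw rate.** n per arm = [1.960√(2p̄q̄) + 1.282√(p₁q₁ + p₂q₂)]²/(p₁ − p₂)², with p₁ = 0.50 and 90% power. For p₂ = 0.26: (1.345 + 0.852)²/0.24² = 84. Power at a true 0.35 with 84 per arm: Φ[(0.15√84 − 1.370)/0.691] = Φ(0.007) = 50%. A true 0.35 needs about 226 per arm. The same steps from the n=30 expected rates give:

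| w | Planning rate | n per arm | Power at 0.35 |
|---|---|---|---|
| 0.25 | 0.3275 | 170 | 80% |
| 0.5 | 0.3057 | 132 | 69.5% |
| 1 | 0.26 | 84 | 50% |

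**8. Which estimate removes the bias.** In a dose-plus-dilution main-effects fit on the rate scale, the chosen cell's fitted value is ¾ of its own rate, plus ¼ of each of the two cells sharing its dose or dilution, minus ¼ of the opposite cell. With excesses −b and +b/3 this is −¾b + b/12 = −⅔b, so −8.8 becomes −5.9 and only a third is removed. The whole-cohort mean has excess (−b + 3 × b/3)/4 = 0.

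**The case against.** The strongest reply is that the 9-point figure belongs to a rule the plan does not use. Selection rests on safety, feasibility and many efficacy outcomes, and Section 1.1.10 puts dose-safety ahead of dose-efficacy. If intubation has little effective weight, the bias is small. This stands, and it is why the result is a range. It does not remove the point. Any positive weight biases in the same direction, and the rule is worded differently in Sections 1.1.1 (a positive dose trend), 1.1.7.3 (efficacy, adverse effects, tolerance) and 1.1.12, so the plan cannot show that the weight is small.

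A reader might infer that Phase III will be mis-sized. The documents do not support that. They say these data inform the effect size, but Aim #3 plans estimates for four schedules, two doses and the whole cohort, and does not say which one will be carried forward.

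A reader might also infer that the trial's efficacy test is invalid. It is not, if done on the whole cohort: the stated evidence is a lower rate in treated infants than a fixed 0.5, and choosing a schedule does not alter that comparison.

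Two further points stand. Most of the 19–20% is ordinary multiplicity, since all pairwise comparisons are planned anyway and about 12% arises without selection. And the sentence about weight and reference is undefined, so treating it as a hypothesis test is a reasonable reading rather than an explicit one. The caveat that the trial is not powered for efficacy is no answer: it concerns missed effects, and small groups make selection bias larger.

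**Conclusion.** The point holds in this form: selecting partly on intubation and then using the winner as reference for intubation in the same infants, without correction, is expected to overstate that schedule's benefit. This is a bias on average, not a certainty in any one trial. At a true rate of 0.35 in all four schedules it runs from about 2 points (weight 0.25) to 9 (intubation alone) at n=30, and from about 2 to 7 at n=50. It is nil if intubation has no effective weight and smaller if true rates differ.

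The Phase III consequence is conditional. Power of about 80%, just under 70% or 50% instead of 90% follows only if the selected raw rate is used for sizing, with a control rate of 0.50. The weights, equal rates, independence and Phase III settings are assumptions of this check. The change is worth making because it is cheap and the plan leaves the size of the bias open.

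**What to change.** In Section 1.1.12:

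1. Name the reference schedule in advance, or code dose and dilution as two factors.
2. Delete the weight based on the data-chosen schedule.
3. State that the effect size carried to Phase III is the whole-cohort estimate, or an estimate shrunk toward the four-schedule mean, with its interval, and not the raw rate of the selected schedule.

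Item 3 is the essential one. A fixed reference cures neither the bias in the selected raw rate nor the multiplicity of the pairwise tests, and a main-effects model alone leaves about two thirds of the bias.

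The cost is wording only; no extra infants or data are needed. The downsides are that the quoted effect for the chosen schedule becomes less favourable, and that a pooled estimate would understate a schedule that is truly better.
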